8.0 Handling of Potential Intercurrent Events for the Primary and Key Secondary Endpoints

The primary efficacy endpoints (defined in Section 3.1) and the ranked secondary endpoint (defined in Section 3.2) in Period A will be analyzed in the ITT_A Population and the following method will be used to address the potential intercurrent event:

- Subjects who receive alternative PsO treatment regardless of premature discontinuation of study drug before Week 16 will be counted as non-responders.

The primary efficacy endpoint (defined in Section 3.1) and ranked secondary endpoints (defined in Section 3.2) in Period B will be analyzed in the ITT_B_NR Population and the following method will be used to address the potential intercurrent events:

- Subjects who receive alternative PsO treatment regardless of premature discontinuation of study drug before Week 52 will be counted as non-responders.
- Subjects who satisfy rescue criteria or receive the rescue medication at Week 28 or Week 40 will be counted as non-responders.

9.0 Efficacy Analyses

9.1 General Considerations

All efficacy analyses will be conducted among the ITT Population in each analysis period. All tests will be 2-sided at an alpha level of 0.05.

The Primary Analysis for Period A will be performed after all ongoing subjects have completed Week 16 and all data pertaining to Period A are cleaned. This will be the only and final analysis for efficacy in Period A.

The Primary Analysis for Period B will be performed after all ongoing subjects have completed Week 52 and all data pertaining to Period B are cleaned. This will be the only and final analysis for efficacy in Period B.

The final analysis will be performed upon study completion.

Categorical Endpoints:

For categorical endpoints, the number and proportion of subjects who achieved the endpoint, as well as the 95% confidence interval (CI) of that proportion, will be provided by each treatment group among all ITT Populations.

In addition, comparisons between treatment groups will be made in the following analyses, with the estimated treatment difference, as well as the corresponding 95% CI and the p-value provided among the following populations:

- ITT_A Population: Comparisons in Period A will be made between RZB and APR using the Cochran-Mantel-Haenszel (CMH) test, adjusting for the actual values of stratification factors at Baseline: Baseline body weight (≤ 100 kg, > 100 kg) and prior exposure to any systemic and/or biologic treatment for psoriasis ($0, \geq 1$). In case of any stratum with zero subject in either treatment group, no stratification factor will be controlled.
- ITT_B_NR Population: Comparisons in Period B will be made between APR/RZB and APR/APR using the chi-square test.

- ITT_B_Combined Population: Comparisons in Period B will be made between APR/RZB and APR/APR using the CMH test, adjusting for the actual values of the stratification factor of re-randomization: PASI 75 response status at Week 16 (Yes/No). In case of any stratum with zero subject in either treatment group, no stratification factor will be controlled.
- ITT_LT Population: Comparisons in Period B will be made between RZB/RZB and APR/APR using the Cochran-Mantel-Haenszel (CMH) test, adjusting for the actual values of stratification factors at Baseline: Baseline body weight (≤ 100 kg, > 100 kg) and prior exposure to any systemic and/or biologic treatment for psoriasis ($0, \geq 1$). In case of any stratum with zero subject in either treatment group, no stratification factor will be controlled.

Continuous Endpoints:

For continuous endpoints, the Baseline mean, visit mean, as well as the Least Square (LS) mean, 95% confidence interval (CI) and Standard Error (SE) of that mean, will be provided by each treatment group among all ITT Populations.

In addition, comparisons between treatment groups will be made in the following analyses, with the estimated treatment difference, as well as the corresponding 95% CI, SE and the p-value will be provided among the following populations:

- ITT_A Population: Comparisons in Period A will be made between RZB and APR based on the fixed term of treatment from a Mixed-effect Model Repeat Measurement (MMRM) model including the Baseline value and observed measurements at all post-baseline visits, adjusting for the fixed effects of treatment, actual values of stratification factors at Baseline, visit and treatment-by-visit interaction as covariates.
- ITT_B_NR Population: Comparisons in Period B comparisons will be made between APR/RZB and APR/APR based on the fixed term of treatment from a Mixed-effect Model Repeat Measurement (MMRM) model including the Baseline value and observed measurements at all post-baseline visits after Entry of Period B, adjusting for the fixed effects of treatment, visit and treatment-by-visit interaction as covariates.

- ITT_Combined Population: Comparisons in Period B comparisons will be made between APR/RZB and APR/APR based on the fixed term of treatment from a Mixed-effect Model Repeat Measurement (MMRM) model including the Baseline value and observed measurements at all post-baseline visits after Entry of Period B, adjusting for the fixed effects of treatment, actual values of stratification factor at re-randomization, visit and treatment-by-visit interaction as covariates.
- ITT_LT Population: Comparisons in Period B comparisons will be made between RZB/RZB and APR/APR based on the fixed term of treatment from a Mixed-effect Model Repeat Measurement (MMRM) model including the Baseline value and observed measurements at all post-baseline visits after Entry of Period B, adjusting for the fixed effects of treatment, actual values of stratification factor at Baseline, visit and treatment-by-visit interaction as covariates.

"Baseline" refers to the last non-missing observation on or before the date of the first administration of study drug, or the date of randomization if no study drug is administered.

"Entry of Period B" refers to the last non-missing observation on or before:

- The first dose date on or after re-randomization, or the date of re-randomization if no study drug is administered in Period B, for subjects who are randomized to APR at Baseline.
- The first dose date on or after Week 16, or the first visit date on or after Week 16 if no study drug is administered in Period B, for subjects who are randomized to RZB at Baseline.

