2.3 Treatment Assignment and Blinding

All subjects will be assigned a unique identification number by the IRT at the screening visit. For subjects who rescreen, the screening number assigned by the IRT at the initial screening visit should be used. The IRT will assign a randomization number that will encode the subject's treatment group assignment according to the randomization schedule.

In Period A (Baseline to Week 16), subjects will be centrally randomized to risankizumab (Arm 1) or apremilast (Arm 2) in a 1:2 ratio at Baseline. Randomization will be stratified

by Baseline body weight (≤ 100 kg, > 100 kg) and prior exposure to any systemic and/or biologic treatment for Po ($0, \geq 1$).

In Period B (Week 16 to Week 52), subjects initially randomized to risankizumab (Arm 1) will continue to receive risankizumab. Subjects initially randomized to apremilast (Arm 2) will be centrally re-randomized at the Week 16 visit in a 1:1 ratio to receive either risankizumab (Arm 2a) or apremilast (Arm 2b). Re-randomization will be stratified by PASI 75 response (responder, non-responder) at Week 16. Rescue risankizumab will be offered to subjects who are re-randomized to apremilast (Arm 2b) and are PASI 50 non-responders at Week 28 (Arm 3a) or Week 40 (Arm 3b).

This is an open-label study; however, the efficacy assessor will remain blinded to each subject's treatment, clinical laboratory results, and all subject safety data during the course of the study.

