9.2.2 Continuous Endpoints

Mixed-Effect Model Repeat Measurement (MMRM) will be the primary and only approach to handle missing data for continuous endpoints among all ITT Populations except for the ITT_Res Population. The MMRM will be conducted using mixed model including observed measurements at all visits, using all available data even if a subject has missing data at some (but not all) post-baseline visits during the analysis period. Subjects' observations after the use of alternative PsO treatment regardless of premature discontinuation of study drug or after the use of RZB as the rescue medication will be excluded from the model. An unstructured variance covariance matrix (UN) will be used. If the model cannot converge, an appropriate covariance structure matrix (e.g., autoregressive (1) or compound symmetry) will be used. The parameter estimations are based on the method of restrictive maximum likelihood (REML). The fixed effects will be used to report model-based means at corresponding visits.

- Comparison of additional endpoints among the ITT_A and ITT_LT Populations will be made adjusting for treatment, visit and treatment-by-visit interaction, actual values of stratification factors at Baseline, and baseline value (if not duplicating the stratification factors).
- Comparison of additional endpoints among the ITT_B_NR Population will be made adjusting for treatment, visit and treatment-by-visit interaction and baseline value.

- Comparison of additional endpoints among the ITT_B_Combined Population will be made adjusting for treatment, visit and treatment-by-visit interaction, actual values of stratification factors at re-randomization, and baseline value (if not duplicating the stratification factors).
- Summary statistics will be provided for additional endpoints among the ITT_B_R Population, adjusting for treatment, visit and treatment-by-visit interaction and baseline value.

Of note, during the Primary Analysis for Period A upon completion of Week 16, the MMRM analysis will only be performed at all visits up to Week 16.

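### Unranked continuous endpoints: the models for the re-randomised arms omit the Week 16 value, the ITT_LT model drops early leavers that its population keeps, and TSQM-9 has no Baseline to adjust for (minor)

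*SAP*

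**What the plan says.** **Re-randomised arms.** SAP 2.3 states: "Re-randomization will be stratified by PASI 75 response (responder, non-responder) at Week 16". The ITT_B_NR model in SAP 9.1 has "including the Baseline value and observed measurements at all post-baseline visits after Entry of Period B, adjusting for the fixed effects of treatment, visit" and the interaction. SAP 9.2.2 agrees: "Comparison of additional endpoints among the ITT_B_NR Population will be made adjusting for treatment, visit and treatment-by-visit interaction and baseline value". The combined model also has Baseline, plus "treatment, actual values of stratification factor at re-randomization, visit and treatment-by-visit interaction as covariates", so Week 16 enters there only as PASI 75 yes/no. SAP 9.1 defines Baseline as the value before first study drug and defines Entry of Period B separately. SAP Appendix D 2.3 uses the Entry value when imputing the binary endpoints.

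**ITT_LT.** SAP 4.0 includes every subject randomised to RZB, the APR/APR subjects, and half of the APR subjects who left the study before Period B. Its MMRM in SAP 9.1 uses Baseline and visits after Entry of Period B. SAP 9.2.2 sets the data rule: "using all available data even if a subject has missing data at some (but not all) post-baseline visits during the analysis period". In the binary analysis, Appendix D 2.3 counts the same leavers as non-responders.

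**TSQM-9.** The activity schedule (protocol Appendix D) ticks TSQM-9 at eight visits, Week 4 to Week 52, and at neither Screening nor Baseline. SAP 3.3 defines two TSQM-9 endpoints: the score at Period A visits, and change from Entry of Period B in re-randomised subjects. The ITT_A model is nevertheless a "model including the Baseline value and observed measurements at all post-baseline visits, adjusting for the fixed effects of treatment, actual values of stratification factors", and the Period B models also carry Baseline, including ITT_B_R: "Summary statistics will be provided for additional endpoints among the ITT_B_R Population, adjusting for treatment, visit and treatment-by-visit interaction and baseline value". Protocol 7.4 qualifies the Baseline term as applying only where applicable for ITT_A and ITT_LT. The SAP does not carry that qualifier.

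**The concern.** For APR/RZB versus APR/APR, Week 16 is the last assessment before randomisation. It is normally the most informative covariate and it is already collected. Leaving it out gives up precision. It also leaves unadjusted any dropout soon after Week 16 that depends on Week 16 status.

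The RZB/RZB versus APR/APR contrast rests on Day 1 randomisation, and ITT_LT was built to respect that by keeping early leavers. A model that starts after Entry of Period B removes them again, so the continuous result compares only subjects who reached Period B. Leavers can appear in the descriptive "the Baseline mean, visit mean, as well as the Least Square (LS) mean" table through their Baseline mean, but in no model-based result.

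For TSQM-9, a covariate that is missing for everyone leaves no usable row. The programmer must then drop the term or substitute another, and these are different models. The SAP does not record the choice.

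**Working it through.** The documents give no correlation, SD or dropout rate for continuous endpoints, and no stated figure to reproduce for them. The nearest plan figures (SAP 2.4) do reproduce: 60 per group at 50% v 20% gives 94.1% power, against the stated more than 90%, and 120/0.55 = 218, stated as 220. The point does not rest on them. All inputs below are assumptions unless a section is named.

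**1. Adding Week 16 to ITT_B_NR**

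With complete data, the variance ratio at Week 52 is (1 − R²)/(1 − rB²), where R² = (rB² + r16² − 2·rB·r16·rBW)/(1 − rBW²). Here rB and r16 are the correlations of Baseline and Week 16 with Week 52, and rBW is the correlation between Baseline and Week 16.

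- Whole APR arm, (rB, r16, rBW) = (0.2, 0.4, 0.4): R² = (0.04 + 0.16 − 0.064)/0.84 = 0.162, and the ratio is 0.838/0.96 = 0.873.
- (0.3, 0.5, 0.5) gives 0.821, and (0.3, 0.6, 0.5) gives 0.703. A 13-30% reduction is therefore an upper limit.
- ITT_B_NR holds only PASI 75 non-responders, taken as the worst 55% at Week 16 (the SAP 2.4 share). In simulation this lowers the Week 16/Week 52 correlations from 0.4, 0.5, 0.6 to 0.26, 0.34, 0.42, and the ratios become 0.941, 0.908, 0.838.
- If switching to RZB also halves the correlations in that arm, the simulated ratios are 0.975, 0.948, 0.912: a 2-9% fall in variance, or 1-5% in SE. If the correlation vanishes after switching, the fall is 1-5%.
- SAP 9.2.2 excludes rows after rescue. Week 28 then carries much of the Week 16 information for rescued subjects. With 30% of APR/APR rescued the gain is 2-7%, and with 50% it is 1-3%.
- If Week 16 predicts nothing, the ratio is 1.009, a loss of about 1%.

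**2. ITT_LT head count and shift**

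For 5/10/15% of 220 APR subjects leaving before Period B:

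| | 5% | 10% | 15% |
|---|---|---|---|
| APR leavers | 11 | 22 | 33 |
| Half kept, even ranks (SAP 4.0) | 5 | 11 | 16 |
| Re-randomised to APR | 104 | 99 | 93 |
| RZB leavers of 110, at 2/3/5% | 2 | 3 | 6 |

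So 5, 11 or 16 of about 110 APR/APR members supply no row, and neither do 2, 3 or 6 RZB members.

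When a share p leaves, the retained arm's mean rises by [p/(1 − p)]·d·r·SD, where d is the leavers' mean shortfall at Week 4 in SDs and r is the Week 4/Week 52 correlation. Assume mean percent PASI improvement at Week 52 of 88 v 45 (difference 43), SD 30 and r = 0.3-0.5.

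- Largest equal-SD case: 15% v 5% leaving, odds ratio of leaving 4 per SD, r = 0.5. Integrating the logistic leaving model gives d = 0.946 (APR) and 1.164 (RZB). APR: 0.1765 × 0.946 × 15 = 2.50. RZB: 0.0526 × 1.164 × 15 = 0.92. Shift = −1.58.
- Smallest: 5% v 2%, odds ratio 2, r = 0.3: shift about −0.2.
- With RZB SD 15 and half the correlation, the largest shift is −2.28.
- If good responders leave instead (odds ratio 0.5), the shift is about +0.2 to +1.4.
- SE in the worst case: 30·√(1/93 + 1/104) = 4.3 with equal SDs, and √(900/93 + 225/104) = 3.4 with unequal SDs. Every shift is below one SE. Rows lost to rescue would widen the SE further.

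An all-visits model brings the shift to about zero if covariances are equal and every leaver has Week 4 data. About half remains if only half of them do. With unequal covariances it removes about 40-45% (−2.28 becomes −1.35).

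**3. TSQM-9**

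Setting SAP 3.3 beside the schedule, no Baseline value exists for either endpoint. The affected models are ITT_A (Period A scores) and ITT_B_NR, ITT_B_Combined and ITT_B_R (change from Entry). No size applies.

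**The case against.** Part 1 can be called preference. Baseline is a natural covariate for change-from-Baseline endpoints, both models are unbiased with complete data, ITT_B_Combined already carries PASI 75 status, and rescue shrinks the gain. All of that stands, and it is why the gain is put at a few percent. It does not remove the gain, since the covariate is free and precedes re-randomisation.

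On ITT_LT, SAP 9.2.2 states its data rule openly, the shift is small and of unknown sign, and the remedy is only partial. That is also right, but the rule conflicts with the purpose for which SAP 4.0 keeps the leavers. Only subjects who leave the study are concerned. Under protocol 5.6, those who merely stop drug should continue to be followed.

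Three stronger readings are tempting and unsupported:

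- A reader might infer that TSQM-9 also breaks the ITT_LT model. SAP 9.5 does send additional endpoints to ITT_LT in general. But the Period B TSQM-9 endpoint is restricted to re-randomised subjects, and RZB/RZB subjects are never re-randomised, so no TSQM-9 endpoint exists for that contrast.
- A reader might infer that every Period B model should adjust for Week 16. In ITT_LT it is measured after randomisation and is itself an outcome of the contrast.
- A reader might infer bias in the randomised Period B comparison. With complete data there is none.

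**Conclusion.** The point holds as a minor one. The ITT_B_NR and ITT_B_Combined models omit a collected covariate that precedes re-randomisation. In ITT_B_NR this is worth about 2-9% of variance without rescue and about 1-7% with 30-50% of APR/APR rescued. The ITT_LT continuous comparison conditions on reaching Period B, with an assumed shift of 0.2-2.3 points on 43. It would understate the RZB advantage if poor responders leave and overstate it if good responders leave. The TSQM-9 models name a value that is not collected. The correlations, SDs, dropout and rescue rates are all assumed; the omissions themselves are plain from the text. Nothing in the testing hierarchy (SAP 13.0) is touched, so no inference about the primary or ranked results follows.

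**What to change.** Make these edits before the Week 52 lock. None needs new data.

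1. **ITT_B_NR and ITT_B_Combined** (SAP 9.1, 9.2.2; protocol 7.4): add the continuous Entry of Period B value beside Baseline. Cost: about 1% of variance if it predicts nothing.
2. **ITT_LT** (SAP 9.1 and the data rule in 9.2.2): use all post-Baseline visits, Week 4 to Week 52, as responses and report the Period B visits. Do not add Week 16 as a covariate. Show the number contributing beside the ITT_LT N. State that leavers with no post-Baseline value stay out, and that the MMRM treats leavers as missing at random while the binary analysis counts them as non-responders. Cost: for PASI the unstructured covariance grows from 6 visits (6·7/2 = 21 parameters) to 8 (8·9/2 = 36), for which 9.2.2 already gives a fallback. The gain is least for BSA, which has no Week 4 assessment.
3. **TSQM-9** (SAP 9.1, 9.2.2): drop the Baseline term in ITT_A, and use the Entry of Period B value in its place in ITT_B_NR, ITT_B_Combined and ITT_B_R. Protocol 7.4 needs the same edit for those three models only. ITT_LT needs no TSQM-9 edit. If the Period A database is already locked, date the ITT_A edit as post-lock and record what was done.

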10.0 Safety Analyses

10.1 General Considerations

Safety data will be summarized among the Safety_A, Safety_B_R, Safety_B_NR, and Safety_LT Populations. Safety summaries will be presented by treatment group. For the safety analysis, subjects are analyzed based on the treatment actually received, determined by the first dose of study drug that the subject received during the specific analysis period.

The overview of TEAEs, and potentially clinically important (PCI) findings in laboratory variables and vital sign variables will also be summarized among the Safety_B_Combined, Safety_Res, and ALL_RZB Populations.

Missing safety data will not be imputed.

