10.3 Analysis of Laboratory Data

Data collected from central and local laboratories, including additional laboratory testing due to an SAE, will be used in all analyses, except for Baseline where SAE-related laboratory assessments on or before the first dose of study drug will be excluded. The clinical laboratory tests defined in the protocol operations manual (e.g., hematology and clinical chemistry) will be summarized.

Mean change from Baseline to each applicable post-baseline visit will be summarized for selected laboratory variables among the Safety_A, Safety_B_R, Safety_B_NR, and Safety_LT Populations. The following descriptive statistics will be presented by treatment groups: number of observations, Baseline mean, visit mean, mean change from Baseline and its standard error, and the 95% confidence interval of the mean change from Baseline.

In addition, laboratory parameters will be tabulated using shift tables from Baseline to minimum and maximum values among Safety_A, Safety_B_R and Safety_B_NR, and Safety_LT Populations categorized by the toxicity grade according to NCI CTCAE Version 4.03¹ of the laboratory used for each sample. A similar shift table will also be provided to summarize shifts from Baseline to the final post-baseline value in each period.

Laboratory abnormalities meeting CTC criteria grade 3 and 4 will be summarized among all safety populations.

Laboratory abnormalities will be evaluated based on Potentially Clinically Important (PCI) criteria ([Appendix C](#)). For each laboratory PCI criterion, the number and percentage of subjects who have a laboratory value meeting the criteria will be summarized. Listings will be provided to summarize subject-level laboratory data for subjects meeting PCI criteria.

In addition, the frequencies and percentages of subjects with post baseline liver specific function test values in ALT/SGPT, AST/SGOT, alkaline phosphatase, and total bilirubin will be categorized as follows:

- ALT > 3.0 × ULN
- ALT > 5.0 × ULN
- ALT > 10.0 × ULN
- ALT > 20.0 × ULN
- AST > 3.0 × ULN
- AST > 5.0 × ULN
- AST > 10.0 × ULN
- AST > 20.0 × ULN
- Alkaline phosphatase > 1.5 × ULN
- Total bilirubin > 1.5 × ULN
- Total bilirubin > 2.0 × ULN
- ALT and/or AST > 3× ULN and Total bilirubin > 1.5× ULN
- ALT and/or AST > 3× ULN and Total bilirubin > 2× ULN
- ALT > 3× ULN and Total bilirubin > 1.5× ULN
- ALT > 3× ULN and Total bilirubin > 2× ULN

The listing will include all subjects who met any of the following four criteria:

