10.4 Analysis of Vital Signs

Vital sign measurements of systolic and diastolic blood pressure will be summarized.

Change from baseline to each applicable post-baseline visit will be summarized for each vital sign variable among the Safety_A, Safety_B_R, Safety_B_NR, and Safety_LT Populations. The following descriptive statistics will be presented by treatment groups: number of observations, Baseline mean, visit mean, mean change from Baseline and its standard error, and the 95% confidence interval of the mean change from Baseline.

Vital sign variables will be evaluated based on potentially clinically important (PCI) criteria ([Appendix C](#)) among all safety populations. For each vital sign PCI criterion, the number and percentage of subjects who have a vital sign value meeting the criteria at least once in each period will be summarized. Listings will be provided to summarize subject-level vital sign data for subjects meeting PCI criteria.

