Appendix C. Potentially Clinically Important Criteria for Safety Endpoints

The criteria for Potentially Clinically Important (PCI) laboratory findings are described in Table C-1 and Table C-2, and the PCI criteria for vital sign findings are described in Table C-3.

Table C-1. Criteria for Potentially Clinically Important Hematology Values

Hematology Variables	Units	Definition of Potentially Clinically Important Current (Version 4) CTCAE Grade 3 or Greater
		Very Low
Hemoglobin	g/dL	< 8.0
Platelets count	10 ⁹ /L	< 50.0
WBC count	10 ⁹ /L	< 2.0
Neutrophils	10 ⁹ /L	< 1.0
Lymphocytes	10 ⁹ /L	< 0.5

Note: A post-baseline value must be more extreme than the baseline value to be considered a potentially clinically important finding.

Table C-2. Criteria for Potentially Clinically Important Chemistry Values

Chemistry Variables	Units	Definition of Potentially Clinically Important Current (Version 4) NCI CTCAE Grade 3 or Greater	
		Very Low	Very High
TBL	mcmol/L		$> 3.0 \times \text{ULN}$
ALP	U/L		$> 5.0 \times \text{ULN}$
SGOT/AST	U/L		$> 5.0 \times \text{ULN}$
SGPT/ALT	U/L		$> 5.0 \times \text{ULN}$
Albumin	g/L	< 20	
Glucose	mmol/L	< 2.2	> 13.9
Triglycerides	mmol/L		> 5.7
Creatinine	mcmol/L		$> 3.0 \times \text{ULN}$ ($> 3.0 \times \text{BL}$)
Sodium	mmol/L	< 130	> 155
Potassium	mmol/L	< 3.0	> 6.0
Calcium	mmol/L	< 1.75	> 3.1
CPK	U/L		$> 5.0 \times \text{ULN}$
Total Cholesterol	mmol/L		> 10.34
GGT			$> 5.0 \times \text{ULN}$

Note: A post-baseline value must be more extreme than the baseline value to be considered a potentially clinically important finding.

Table C-3. Criteria for Potentially Clinically Important Vital Sign Values

Vital Signs Variables	Criterion	Definition of Potentially Clinically Important
Systolic Blood Pressure (mmHg)	Low	Value ≤ 90 mmHg and decrease ≥ 20 mmHg from Baseline
	High	Value ≥ 160 mmHg and increase ≥ 20 mmHg from Baseline
Diastolic Blood Pressure (mmHg)	Low	Value ≤ 50 mmHg and decrease ≥ 10 mmHg from Baseline
	High	Value ≥ 100 mmHg and increase ≥ 10 mmHg from Baseline

Appendix D. Non-Responder Imputation Incorporating Multiple Imputation to Handle Missing Data Due to COVID-19 Pandemic for Dichotomized Outcome Variables

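### In ALL_RZB and Safety_Res, PCI laboratory and blood-pressure findings are judged against a Baseline that predates 16 to 40 weeks of apremilast for switched and rescued subjects

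*SAP*

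**What the plan says.** SAP Section 9.1 defines Baseline once: it "refers to the last non-missing observation on or before the date of the first administration of study drug". For anyone randomised to apremilast, that dose is apremilast on Day 1. The definition stands in the efficacy section, but Section 10 gives no other. Section 10.3 uses the same anchor when it says which laboratory samples count, "except for Baseline where SAE-related laboratory assessments on or before the first dose of study drug will be excluded".

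Section 10.1 states that PCI findings in laboratory and vital-sign variables "will also be summarized among the Safety_B_Combined, Safety_Res, and ALL_RZB Populations". Section 10.4 adds that "Vital sign variables will be evaluated based on potentially clinically important (PCI) criteria", and applies this to every safety population.

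The criteria are in Appendix C. The laboratory tables set cut-offs at CTCAE Grade 3 or greater, with the note "A post-baseline value must be more extreme than the baseline value to be considered a potentially clinically important finding". Creatinine also carries a multiple-of-baseline criterion. The blood-pressure table asks for a level and a change together, for example "Value ≥ 160 mmHg and increase ≥ 20 mmHg from Baseline" for high systolic pressure.

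Section 9.1 also defines an Entry of Period B reference, but it serves efficacy analyses only. The SAP defines no reference before rescue.

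**The concern.** ALL_RZB is the SAP's comprehensive safety summary for risankizumab, and Safety_Res describes rescued subjects once they are on risankizumab. Neither has a concurrent comparator arm, so a reader will take a PCI count in these tables as something seen on risankizumab relative to the state before it.

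For switched and rescued subjects the reference is instead the state before apremilast. Whatever changed on apremilast and persisted is included in the comparison, and whatever improved on apremilast and then reversed may be hidden.

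The SAP is also inconsistent across these summaries. For the same two populations, adverse events (Section 10.2.1), treatment duration (Section 6.0) and patient-years (Section 10.2.4) all start at the first risankizumab or first rescue dose. Only the Baseline-dependent PCI findings keep the earlier anchor.

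**Working it through.** **1. Which summaries are exposed.**

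| Summary (SAP section) | Planned for Safety_Res and ALL_RZB? | Compared with Baseline? | Counting starts at |
|---|---|---|---|
| TEAEs (10.1, 10.2.1) | Yes | No | First rescue or first risankizumab dose |
| Duration, patient-years (6.0, 10.2.4) | Yes | No | First rescue or first risankizumab dose |
| PCI laboratory (10.1, 10.3, App. C) | Yes | Yes, must be more extreme | Not stated |
| PCI blood pressure (10.1, 10.4, App. C) | Yes | Yes, set change required | No risankizumab window stated |
| Grade 3 and 4 laboratory (10.3) | Yes: "Laboratory abnormalities meeting CTC criteria grade 3 and 4 will be summarized among all safety populations" | None stated | Not stated |
| Mean change, laboratory and vital signs; laboratory shift tables (10.3, 10.4) | No | Yes | Not applicable |

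The last row rests on text such as "Mean change from Baseline to each applicable post-baseline visit will be summarized for selected laboratory variables among the Safety_A, Safety_B_R, Safety_B_NR, and Safety_LT Populations", which leaves out both populations. The Baseline problem is therefore confined to the two PCI rows.

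**2. How old the reference is.** Under protocol Section 4.1, switching happens at Week 16 and rescue at Week 28 or Week 40. The Day 1 reference is thus 16, 28 or 40 weeks old at the first risankizumab dose.

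**3. Worked cases** (hypothetical values, Appendix C rules):

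| Variable | Day 1 | On apremilast, before first risankizumab dose | On risankizumab | Against Day 1 | Against pre-risankizumab value |
|---|---|---|---|---|---|
| Triglycerides, mmol/L (cut-off > 5.7) | 2.0 | 6.0 | 5.9 | PCI (5.9 > 2.0) | Not PCI (5.9 < 6.0) |
| Systolic, mmHg | 140 | 158 | 160 | PCI (160 − 140 = 20) | Not PCI (160 − 158 = 2) |
| Systolic, mmHg | 150 | 138 | 162 | Not PCI (162 − 150 = 12) | PCI (162 − 138 = 24) |

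The first two are over-attribution. The third is a missed worsening.

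**4. Illustrative size for systolic pressure.** All inputs are assumed, and there is no risankizumab effect: mean 130 mmHg, between-subject SD 14, visit SD 9, a persistent apremilast-period shift with SD 6, and five visits on risankizumab. (A switched subject has six scheduled visits after Week 16; a subject rescued at Week 28 has four.) The proportion with at least one PCI-high value was:

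| Mean shift on apremilast | Day 1 reference | Pre-risankizumab reference |
|---|---|---|
| 0 mmHg | 5.0% | 3.5% |
| +3 mmHg | 8.0% | 4.5% |
| +6 mmHg | 11.9% | 5.6% |

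The documents give no blood-pressure data, so this shows only how the rule behaves. It is not a forecast.

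**5. Share of ALL_RZB that enters through apremilast.** The plan's allocation first: 120/0.55 = 218.2, stated as 220 on apremilast; 110 + 220 = 330. Let *d* be the share of the apremilast arm lost before Week 16 and *q* the share of the continuing apremilast arm that is rescued. The documents give neither. With 1:1 re-randomisation and all 110 initial risankizumab subjects dosed:

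- switched *s* = 220(1 − *d*)/2; rescued *r* = *q* × *s*
- share = (*s* + *r*)/(110 + *s* + *r*)

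| *d* | *q* = 0 | *q* = 1 |
|---|---|---|
| 0 | 110/220 = 50.0% | 220/330 = 66.7% |
| 0.10 | 99/209 = 47.4% | 198/308 = 64.3% |
| 0.20 | 88/198 = 44.4% | 176/286 = 61.5% |

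With 10% to 20% loss, the range is 44% to 64%.

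**6. Whether a later reference value exists** (protocol Appendix D). Vital signs are taken at every clinic visit. The last scheduled laboratory values before the first risankizumab dose are:

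| First risankizumab dose | Hematology | Electrolytes, lipids | Other chemistry |
|---|---|---|---|
| Week 16 (switch) | Week 16 | Week 16 | Week 16 |
| Week 28 (rescue) | Week 16 | Week 16 | Week 20 |
| Week 40 (rescue) | Week 32 | Week 16 | Week 32 |

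**The case against.** **Laboratory counts would move little.** These criteria are essentially absolute Grade 3 cut-offs, and Baseline only adds that the value be more extreme. Changing the reference removes a laboratory finding only if the last pre-risankizumab value was at least as extreme, and so itself beyond the cut-off. Screening limits in protocol Section 5.1 make such values unlikely at entry for ALT, AST, hemoglobin, platelets, white cells and neutrophils, and confirmed marked ALT or AST elevations lead to evaluation and possible discontinuation under Section 5.5. This stands, and is why blood pressure is the main concern.

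**The populations are descriptive, and a drug-free reference is a recognised convention.** No hypothesis is tested in either population, and subject-level listings are planned for everyone who meets PCI criteria. That softens the consequence, but the summary counts would still answer a different question from the adverse-event counts beside them.

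**The randomised Period B comparison is not biased in this way.** A reader might extend the point to APR/RZB against APR/APR. In Safety_B_NR, Safety_B_R and Safety_B_Combined both arms share the pre-apremilast reference and were re-randomised after the same 16 weeks, so the point does not carry over.

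**A reader might infer that all risankizumab safety findings are misattributed.** The SAP does not support that. Adverse events with onset before the first risankizumab dose are excluded from the rescue and ALL_RZB sets, and mean-change and shift tables are not planned for either.

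**Conclusion.** The point holds for PCI laboratory and blood-pressure findings in ALL_RZB and Safety_Res, and for nothing wider. Followed as written, the SAP would count some changes that began on apremilast as risankizumab findings and would miss some worsening on risankizumab. The effect falls mainly on the blood-pressure criteria, which need a set change from Baseline.

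It is tempting to conclude that the rule is wrong for most of ALL_RZB. Two things stand against that. The 44% to 64% is the share of subjects to whom the early reference applies, not the share of findings misclassified, which the documents do not allow anyone to estimate. Nor is a majority assured: with no rescue and 10% to 20% loss before Week 16, the share is 44% to 47%.

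Efficacy results and type I error control are not touched. The change is worth making because these tables are uncontrolled and the SAP already dates its other risankizumab summaries from the first risankizumab dose.

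**What to change.** For PCI summaries in ALL_RZB and Safety_Res, define baseline in SAP Sections 10.3 and 10.4 and Appendix C as the last non-missing value on or before the first risankizumab dose. For subjects first randomised to risankizumab, nothing changes. Count only values after that dose, in line with the TEAE window, which ends 140 days after the last risankizumab dose. The grade 3 and 4 laboratory summary could state the same window, since it now has none.

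The cost is SAP wording and one extra derived baseline; no new data are needed. The limit is the laboratory schedule in rescued subjects. Before a Week 28 rescue, the last scheduled hematology is 12 weeks old (28 − 16). The last scheduled electrolytes and lipids are 12 weeks old before a Week 28 rescue and 24 weeks old (40 − 16) before a Week 40 rescue. Attribution for those parameters would improve only in part, and a table footnote should say so. Blood pressure has no such gap, because vital signs are taken at every clinic visit.
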